#### Table 8-4 Assessment of Pharmacologic Therapies and/or Medical Procedures

Assessment	Timing	Measurement
Pharmacologic intervention (ie, anticoagulation, antiarrhythmic drugs)	Through Day 367	
 
Timing of prescription and whether it was prescribed due to occurrence of POAF
 
Length of prescription
 
Timing of AF resolution, if available
 

Procedural intervention (ie, cardioversion, pacemaker implantation, ablation, additional cardiac surgery)	Through Day 367	
 
Timing of procedure and whether it was assigned due to the occurrence of POAF
 
Timing of AF resolution, if available
 

AF = atrial fibrillation; POAF = post-operative atrial fibrillation

A composite endpoint composed of pharmacologic and procedural interventions will also be analyzed.

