8.0 Demographics and Other Baseline Characteristics

Demographic parameters (age; age group; race; ethnicity; sex), baseline characteristics (weight; height; and body mass index, calculated as weight [kg]/(height [m])²), waist circumference (m), and other disease characteristics (type of surgery and number of grafts) will be summarized descriptively by treatment group for the safety population. Continuous variables will be summarized by number of participants and mean, SD, first quartile (Q1), median, minimum, third quartile (Q3), and maximum values. Categorical variables will be summarized by number and percentage of participants.

Medical history data will be coded using the Medical Dictionary for Regulatory Activities (MedDRA). The number and percentage of participants with medical history ongoing at screening will be summarized by system organ class, preferred term, and treatment group for the safety population. Data for medical history that is not ongoing at screening will be summarized and presented in a similar manner. An overall total will be provided for the study as well as by treatment group.

Prior medication is defined as any medication taken before the study treatment. Concomitant medication is defined as any medication taken on or after the day of study treatment.

Both prior and concomitant medications will be coded using the Anatomical-Therapeutic-Chemical classification text from World Health Organization (WHO) Drug Dictionary. The use of prior and concomitant medications will be summarized by the number and percentage of subjects in each treatment group for the safety population. If a participant took a specific medication multiple times or took multiple medications within a specific therapeutic class, that participant would be counted only once for the coded drug name or therapeutic class.

In addition to summarizing all medications as discussed above, a separate tabulation will also be provided for the following medications of interest:

- The following antiarrhythmics: quinidine, procainamide, disopyramide, mexiletine, flecainide, propafenone, amiodarone (including amiodarone hydrochloride, amiodarone hydrochloride w/ glucose and amiodarone;glucose), dronedarone, dofetilide, sotalol (including sotalol hydrochloride), and ibutilide.
- The following anticoagulants: warfarin (including warfarin sodium), dabigatran, apixaban, rivaroxaban, and edoxaban (including edoxaban tosilate).

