Concurrent procedures will be presented in a listing. A tabulation will be provided for concurrent procedures performed due to atrial fibrillation or atrial flutter. Concurrent procedures performed

due to atrial fibrillation or atrial flutter may include: alcohol septal ablation, cardiac ablation, cardioversion, and additional cardiac surgery. See Section 10.3 below for additional discussion of concurrent procedures performed due to atrial fibrillation or atrial flutter.

Additional medications or concurrent procedures meeting the classifications above may be added at the discretion of the clinical team prior to the interim database lock for the primary analysis.

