The following five binary (yes/no) variables will be used to analyze the need for pharmacologic and/or procedural intervention due to AF during the first 30 days post-surgery:

- 1. at least one pharmacologic intervention (i.e., anticoagulation or antiarrhythmic drugs)?
- 2. at least one anticoagulation pharmacologic intervention?
- 3. at least one antiarrhythmic pharmacologic intervention?
- 4. at least one procedural intervention (see list in Section 8.0)?
- 5. at least one pharmacologic or procedural intervention?

In addition, time to event variables will also be created for each of the corresponding 5 variables above. The time to the first event will be used for analysis. All these variables will be analyzed using the same methods for similar variables in Sections 10.1 and 10.2.

The need for pharmacologic and/or procedural intervention due to AF from Day 31 to Day 360 post-surgery will be analyzed in a similar fashion. Participants with no events who exit the study prior to Day 360 will be censored at their respective study exit day minus 30 days, while participants with no events who exit the study on or beyond day 360 will be censored at day 330 (360 - 30 = 330). Pharmacologic and/or procedural interventions due to AF with onset dates prior to day 31 that are ongoing at day 31 will count as events for these endpoints, with a time-to-event equal to zero.

Descriptive statistics will be presented by treatment group for each of the following:

- time to POAF resolution from first dose of prescription of pharmacologic intervention
- time to POAF resolution from first procedural intervention
- types of pharmacologic interventions used due to POAF

- will be further categorized by "medication of interest" (antiarrhythmics versus anticoagulants) as defined in Section 8.0 above.
- yes/no: Beta blocking agent (ATC code: C07A) withdrawn within 3 days post-surgery and no replacement (no new beta blocker prescription) within 7 days post-surgery

Other Efficacy Variables

- Percentage of participants with clinically important tachycardia in AF (defined as heart rate ≥ 100 bpm for at least 2 minutes) within 30 days post-surgery
- Percentage of participants with any occurrence of AF as defined in the primary and secondary endpoints during the first 7 days following Day 60, Day 90, Day 180, Day 270, and Day 360 visits

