- Percentage of participants with at least 1 event of symptomatic AF (symptoms occurring within 2 hours of an AF episode) during the first 7 days following Day 60, Day 90, Day 180, Day 270, and Day 360 visits
- Percentage of participants with actionable AF within 30 days post-surgery. Actionable AF is defined as meeting at least one of the following conditions: hospitalization due to AF, or medicinal or procedural intervention due to AF
- Percentage of participants discharged from hospital (after initial care of indication under study) without prescription of any of the medication of interest listed in Section 8.0
- Percentage of participants free from AF through 12 months post-surgery and not taking any antiarrhythmic drugs (as defined in Section 8.0)
- Percentage of participants free from AF through 12 months post-surgery and not taking any anticoagulant drugs (as defined in Section 8.0)
- Percentage of time spent in AF (AF burden) during the first 7 days following Day 60, Day 90, Day 180, Day 270, and Day 360 visits

The first 6 variables above will be analyzed using the same method used to analyze the primary efficacy variable in Section 10.1. Similarly, the AF burden will be analyzed using the same method discussed in Section 10.2. In addition, descriptive statistics of the AF Burden, including tertiles, will be presented by treatment group. For symptomatic AF, symptoms that occur in the interval that starts two hours prior the onset of the AF episode and ends two hours after the conclusion of the AF episode will meet the definition of "within 2 hours of an AF episode". The date and time when a symptom is experienced is marked by a participant pressing a button on the ePatch itself.

Page 22

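### The discharge-without-medication endpoint counts listed drugs for any indication, which shrinks its risk difference, odds ratio and power (minor; additional endpoint only)

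*SAP*

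**What the plan says.** SAP 10.3, under Other Efficacy Variables, defines success as being "discharged from hospital (after initial care of indication under study) without prescription of any of the medication of interest listed in Section 8.0". The lists are in SAP 8.0, where "a separate tabulation will also be provided for the following medications of interest". They are lists of drug names, for example: "The following anticoagulants: warfarin (including warfarin sodium), dabigatran, apixaban, rivaroxaban, and edoxaban (including edoxaban tosilate". No indication is attached.

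Neighbouring items are worded differently:
- In SAP 8.0, procedures do carry the condition: "A tabulation will be provided for concurrent procedures performed due to atrial fibrillation or atrial flutter".
- In SAP 10.3, five binary variables "analyze the need for pharmacologic and/or procedural intervention due to AF during the first 30 days post-surgery".
- Actionable AF, the bullet just above the discharge endpoint, requires "hospitalization due to AF, or medicinal or procedural intervention due to AF".
- The fourth win-ratio component is likewise limited to interventions due to AF.

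The discharge endpoint is fifth in its list. The SAP assigns the first six variables the primary method, the CMH test stratified by valve surgery and age group, with no multiplicity adjustment (SAP 10.0, 10.1, 10.3). The seventh is the percentage "free from AF through 12 months post-surgery and not taking any anticoagulant drugs (as defined in Section 8.0". Its drug part also lacks an indication condition, and it falls outside the six that are assigned that test.

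The data needed for a narrower definition are collected. Protocol 6.5.2 records indication and start and end dates for every medication. Protocol Table 8-4 records "Timing of prescription and whether it was prescribed due to occurrence of POAF".

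**The concern.** The additional objective is to show clinical benefit, and this treatment works by preventing post-operative AF. A prescription that would have been written with or without post-operative AF carries no information about that.

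The protocol makes such prescriptions possible:
- Valve repair or replacement is eligible (inclusion 2.01) and is a randomisation stratum.
- A history of paroxysmal AF is acceptable (inclusion 6.01).
- Anticoagulants are absent from the washout table (Table 6-2).
- Anticoagulation is given to anyone in whom it is indicated, by local standards (6.5.5), not only to those with POAF.

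Each such participant is a failure in whichever arm he or she falls. A real effect on AF-driven prescribing would then show as a smaller absolute difference and a weaker test.

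**Working it through.** **Plan's own figure.** The documents give no rate or power for this endpoint. As a check on the power formula, the primary assumptions (47.8% versus 27.8%, 100 per arm, two-sided 0.05) give 83.6% with the uncorrected two-proportion formula, 79.6% with continuity correction and 79.7% with Fisher's exact test. The last two match the stated 80% or so. The uncorrected formula is used below.

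**Inputs, all assumed:**
- AF-driven listed prescription at discharge: p = 0.30 placebo, 0.18 active.
- Valve share: v = 0.30 to 0.50.
- Listed drug for a non-AF reason among valve participants: w = 0.40 to 0.80. It is taken as zero elsewhere, equal in all arms and independent of AF.

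**Model.** P(discharged without a listed drug) = (1 − p)(1 − vw). The risk difference is therefore 12 points × (1 − vw). In the ratio of drug-free proportions the factor (1 − vw) cancels.

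| v | w | Drug-free, placebo | Drug-free, active | Difference (points) | RR of being drug-free | CMH power |
|---|---|---|---|---|---|---|
| – | 0 | 70.0% | 82.0% | 12.0 | 1.17 | 51% |
| 0.30 | 0.40 | 61.6% | 72.2% | 10.6 | 1.17 | 38% |
| 0.30 | 0.80 | 53.2% | 62.3% | 9.1 | 1.17 | 35% |
| 0.50 | 0.40 | 56.0% | 65.6% | 9.6 | 1.17 | 31% |
| 0.50 | 0.80 | 42.0% | 49.2% | 7.2 | 1.17 | 25% |

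The relative risk is 0.82/0.70 = 1.17 in every row, and also within each stratum. In the last row's valve stratum it is (1 − 0.836)/(1 − 0.86) = 0.164/0.140 = 1.17.

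**Odds ratio.** The odds ratio for being drug-free is (0.82/0.18)/(0.70/0.30) = 1.95 undiluted. Unstratified, it falls to (0.7216/0.2784)/(0.616/0.384) = 1.62 in the first diluted row and (0.492/0.508)/(0.42/0.58) = 1.34 in the last.

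**Stratified power, last row, 50 per arm in each surgery stratum (age ignored).** Prescription rates are 0.86 versus 0.836 in the valve stratum and 0.30 versus 0.18 otherwise.
- CMH numerator: 25 × 0.024 + 25 × 0.12 = 3.6.
- Null variance: 12.5 × 2 × (0.848 × 0.152 + 0.24 × 0.76) = 7.78, so SD 2.79.
- Variance under the alternative: 12.5 × (0.2575 + 0.3576) = 7.69, so SD 2.77.
- Power: Φ[(3.6 − 1.96 × 2.79)/2.77] = Φ(−0.67) = 25%.

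**Second set of assumptions.** Suppose every POAF participant, and no one else, receives a listed drug for AF, so that the planning rates apply (20 points). With overall non-AF rates of 10%, 20%, 30% and 50%, the difference becomes 18, 16, 14 and 10 points, and unstratified power falls from 84% to 73%, 62%, 51% and 33%.

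**The case against.** The strongest reply is that the question about AF-attributed drugs is already answered. SAP 10.3 has AF-attributed binary variables for anticoagulants and antiarrhythmics separately, time-to-event versions, Day 31 to 360 versions, actionable AF and a win-ratio component. A measure that does not depend on anyone's attribution could be a deliberate complement. This stands in part: the overlap is real and it limits the importance of the point. But none of those variables describes status at discharge, and the SAP does not say that counting every indication is intended.

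Two further replies stand in full. The rates are not in the documents: there is no valve share, and no statement that valve participants usually leave on a listed drug or that antiarrhythmics are given prophylactically. And any bias is toward no difference, so a false claim of benefit is not at stake.

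Stronger readings that a reader might infer do not hold:
- **The relative risk is diluted.** In the assumed scenarios the relative risk of *being prescribed* a drug moves from 0.60 to between 0.72 and 0.88. But the endpoint is the complement, and the relative risk of being drug-free stays at 1.17. SAP 10.1 reports relative risks, so the result is not uninterpretable.
- **Power falls to 17-35%.** That is the unstratified calculation. The planned test stratifies by valve surgery, where this model places the noise, and recovers some of the loss.
- **Both 12-month variables need an indication filter.** The protocol's rationale for exclusion 2.01 treats antiarrhythmics as able to obscure efficacy, without reference to why they are given. Someone free of AF while taking one for another reason is not a clean success, so any-indication is defensible there.

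**Conclusion.** The point holds as a minor improvement. As written, the discharge endpoint scores as failures prescriptions that preventing post-operative AF could not have changed, and it departs from the AF-attributed wording used around it. If non-AF prescribing is balanced across arms, as randomisation should make it on average, the cost is sensitivity. Under the first set of assumptions the difference falls from 12 points to between 10.6 and 7.2, and stratified power falls from about 51% to between 38% and 25%. Power is modest even undiluted. The direction follows from the definition, but the size rests wholly on assumed rates. This is one unadjusted additional endpoint, and nothing here touches the primary or secondary endpoints.

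**What to change.** In SAP 10.3, analyse the percentage discharged without any Section 8.0 medication that was newly prescribed after surgery and is recorded as due to POAF (fibrillation or flutter). Report the any-indication percentage beside it as a descriptive row. Both conditions are needed: filtering on an AF or flutter indication alone would still count anticoagulation for paroxysmal AF that pre-dated surgery.

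Apply the same filter to the anticoagulant part of the 12-month variable on freedom from AF without anticoagulants. Leave the 12-month antiarrhythmic variable as any-indication.

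The cost is SAP wording and a filter on indication, start date and POAF attribution, all of which the protocol already collects. The small downside is reliance on the blinded investigator's attribution, which the need-for-intervention variables in SAP 10.3 already accept. The descriptive row keeps the attribution-free figure visible.

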## 4. Study Design

## 4.1. Overall Design

This is a multi-center, randomized, double-blind, placebo-controlled, parallel group, dose-ranging study to evaluate the efficacy and safety of botulinum toxin type A (AGN-151607) injections into the epicardial fat pads, foci of ganglionic plexi, to prevent POAF in participants undergoing open-chest cardiac surgery. It is projected that a total of approximately 20 to 40 sites (North America and Europe) will enroll a total of approximately 330 participants for this Phase 2 study.

There will be a total of 3 intervention arms randomized in 1:1:1 fashion to receive a one-time injection of:

- 125 U of AGN-151607 (25 U per fat pad)
- 250 U of AGN-151607 (50 U per fat pad)
- Placebo

The randomization will be stratified by age ( $< 65, \ge 65$  years) and type of surgery (presence/absence of valve surgery).

This study intervention will be the administration of a one-time injection of either placebo or AGN-151607 during the open-chest surgery. Primary and secondary efficacy assessments will be performed through Day 30. Additional and exploratory assessments will be assessed through Day 367. All participants will be followed through Day 367 for safety assessments. POAF usually occurs within 2 to 5 days of surgery. However, Pokushalov et al (Pokushalov 2015), found in their study that episodes of POAF were recorded up to 18 days after surgery. Therefore, a 30-day cut off for the primary endpoint is appropriate to mostly fully capture occurrences of POAF. Assessments of clinical benefits and resource-utilization are customarily over a period of 60 days post-surgery (Gillinov 2016). Accordingly, a 60-day cut off was selected for this study to capture resource-utilization outcomes. Finally, based on prior clinical data, the effect of botulinum toxin type A is estimated to be 3 to 6 months. There will be a 12-month follow-up for the study.

Inflammation plays a key role in the etiology of multiple cardiac conditions including the development of POAF. The mechanism of action of AGN-151607

Approximately 400 participants will be screened to achieve approximately 330 randomly assigned to study intervention, in order to have an estimated 300 participants complete all the efficacy assessments up to Day 60 (100 participants per intervention group; Section 9.2).

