10.3 Additional Efficacy Variables

Hospital and ICU Length of Stay

Hospital length of stay for the initial care of indication under study is defined as the time (days) from ICU admission date/time to the date/time of discharge from the hospital. ICU length of stay is defined as the time (hours) from the ICU admission date/time to the date/time of discharge from the ICU. For participants not admitted to the ICU, ICU length of stay will be set to zero and hospital length of stay will be defined as the time (days) from end date/time of study drug administration to date/time of discharge from hospital. For subjects missing ICU admission date/time, ICU admission date/time will be imputed to the end date/time of study drug administration. The date/time of death will be used to derive hospital length of stay for participants who died at the hospital (and ICU length of stay, for participants who die in the ICU).

Descriptive statistics (n, mean, SD, Q1, median, Q3, min, max) for hospital and ICU length of stay will be presented by:

- treatment group
- region (U.S. versus non-U.S.) and treatment group
- country and treatment group
- sites and treatment group

Between-group treatment comparisons in hospital and ICU length of stay will be performed for each AGN-151607 treatment arm versus placebo using the following methods:

- An ANOVA model with treatment group, type of surgery, age group, and region as factors
- An ANOVA model with treatment group and region as factors
- An ANOVA model with treatment group and country as factors

- A stratified Wilcoxon (Van Elteren) test, stratified by type of surgery, age group, and region
- A stratified Wilcoxon (Van Elteren) test, stratified by type of surgery and age group

Descriptive statistics of hospital length of stay measured from the time of initial hospital admission to discharge will be presented by:

- treatment group
- region (U.S. versus non-U.S.) and treatment group
- country and treatment group
- sites and treatment group

ANOVA models, as described above, will be used to estimate confidence intervals for difference in mean hospital length of stay measured from the time of initial hospital admission between each AGN-151607 treatment arm and placebo.

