- A negative binomial (NB) regression model will be used to model the number of AF events (using \geq 30 seconds definition of AF) within 30 days post-surgery, with treatment, type of surgery, and age group as factors and log(total analyzable time) as the offset in the model. A zero-inflated negative binomial (ZINB) regression model will also be estimated with treatment, type of surgery, and age group as factors in both the main and zero-count models and log(total analyzable time) as the offset. If p < 0.05 for the Scaled Pearson chi-square goodness of fit statistic for the NB model (suggesting overdispersion may be present), then the ZINB model will be considered the primary analysis; otherwise, the NB model will be considered the primary analysis. Sensitivity analyses of the number of AF events using Poisson regression and zero-inflated Poisson regression using similar models will be performed. Least squares (LS) mean differences and incidence rate ratios with 95% CIs will also be performed based on the SEA-30 set using the same models.
- The win ratio unmatched approach (Pocock et. al., 2012) will be used to analyze the following composite endpoint:
 - 1. Death
 - 2. Stroke
 - 3. All-cause 30-day rehospitalization
 - 4. Use of pharmacologic or procedural intervention of interest due to AF
 - 5. Hospital length of stay

The components of the endpoints are listed in order of clinical importance. The win ratio, with the associated 95% CI and p-value will be presented for the composite endpoint, as well as for each of the component endpoints. Two win ratios analyses will be performed. The first will analyze binary outcomes for each of the components (with the fifth component being "Hospital length of stay > median hospital length of stay for the total study population"). The second will analyze time-to-event outcomes for each of the components (with the time-to-first-event used for components with multiple events experienced, and with the fifth component being time-to-hospital-discharge from initial care). A list of Medical Dictionary for Regulatory Activities (MedDRA) preferred terms for stroke will be provided by the clinical team. All-cause 30-day rehospitalization includes any hospitalization within 30 days of (first) discharge from the hospitalization for initial care.

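### The binary win ratio in SAP 10.3 reduces length of stay to a split at the pooled median, and neither win ratio uses the randomisation strata: a modest, cheaply avoided loss of power in an additional analysis

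*SAP*

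**What the plan says.** Under Additional Efficacy Variables, SAP 10.3 applies "The win ratio unmatched approach" to a five-level hierarchy: death, stroke, all-cause rehospitalisation within 30 days of discharge, pharmacologic or procedural intervention due to AF, and hospital stay. It adds: "The components of the endpoints are listed in order of clinical importance".

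"Two win ratios analyses will be performed".
- The first is binary throughout, and its last component is "Hospital length of stay > median hospital length of stay for the total study population".
- The second is time-to-event, "with the fifth component being time-to-hospital-discharge from initial care".

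A win ratio, confidence interval and p-value are planned for the composite and for each component. No stratification is mentioned for either analysis, and no direction of a win is written for any component.

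Elsewhere the randomisation factors are used. Protocol 4.1 states "The randomization will be stratified by age", with presence or absence of valve surgery as the second factor. The CMH test (SAP 10.1), the AF-burden and log-rank tests (10.2), the negative binomial model (10.3) and the quality-of-life mixed model (10.4.2) all account for both. For stay on its own, 10.3 includes "A stratified Wilcoxon (Van Elteren) test, stratified by type of surgery and age group".

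**The concern.** A win ratio needs only an ordering within each pair, so it can use length of stay at full resolution. Splitting it at the median discards the ordering of any two stays on the same side, so a stay just above the median ties with one that is weeks longer. The words for the cut-point cover the whole study, which takes in all three arms, so a 125 U versus placebo score also depends on stays in the 250 U arm.

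Without strata, each treated participant is compared with every placebo participant, including across surgery types and age groups. If those factors predict stay and AF intervention, such pairs add noise that the plan's other analyses remove.

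What is at stake is the precision of the only analysis that ranks all five outcomes together.

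**Working it through.** **1. The plan's own figure.** The documents give no power, rate or effect for the win ratio. Their one power statement is for the primary endpoint (SAP 13.0: 100 per arm, 47.8% versus 27.8%, two-sided 0.05, about 80%). Per-arm n without continuity correction is [1.96·√(2·0.378·0.622) + 0.842·√(0.478·0.522 + 0.278·0.722)]² / 0.20² = 91.1, so 92. The continuity correction gives 101, and at n = 100 the power is 79.6%. The figure reproduces, but it says nothing about the composite.

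**2. Ties caused by the split.** Let q₁ and q₂ be the proportions above the cut-point in the two arms. A pair that reaches stay remains tied with probability q₁q₂ + (1−q₁)(1−q₂). With both near one half this is about 0.5.

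**3. Efficiency of a median split.** For normal data (lognormal stay after taking logs), the efficiency of the median test relative to the rank test is (2/π)/(3/π) = 0.67. For logistic data it is 0.75. For the stay component alone, with 100 per arm and a shift of d standard deviations, approximate power is Φ(d·√50·√(3/π) − 1.96) for ranks and Φ(d·√50·√(2/π) − 1.96) for the split:
- d = 0.3: 54.5% against 39.5%
- d = 0.5: 93.3% against 80.5%

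**4. Simulation of the full hierarchy.** All of these inputs are assumed: 100 per arm; death 2%, stroke 2%, rehospitalisation 12%; AF intervention 35% on placebo; lognormal stay with median 7 days and log-SD 0.40; treatment shift 0.3 to 0.5 log-SD (0.3 × 0.40 = 0.12, about 11% shorter; 0.5 × 0.40 = 0.20, about 18% shorter); strata effect per factor 0.15 (moderate) or 0.30 (strong) on log-stay, and twice that on the AF logit. The test is on the log win ratio with U-statistic variance at two-sided 0.05. Strata are pooled with weights nm/(n+m). There were 3,000 to 5,000 replicates, so the Monte Carlo standard error is at most about 0.9 points. The last six columns are composite power in %.

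| Shift; strata effect; AF intervention | Reach stay | Left tied | Binary, split | Split + strata | Binary, actual stay | Actual stay + strata | Time-to-event | Time-to-event + strata |
|---|---|---|---|---|---|---|---|---|
| 0.3; 0.15; 35 v 22% | 42.4% | 21.1% | 41.7 | 41.2 | 49.0 | 49.5 | 43.4 | 43.3 |
| 0.3; 0.30; 35 v 22% | 42.1% | 21.2% | 37.3 | 40.8 | 43.8 | 50.2 | 38.3 | 43.1 |
| 0.5; 0.15; 35 v 22% | 42.4% | 20.7% | 60.8 | 60.4 | 72.0 | 73.4 | 63.9 | 64.6 |
| 0.4; 0.15; 35 v 35% | 39.6% | 19.6% | 11.1 | 11.1 | 18.2 | 18.4 | 12.5 | 12.7 |

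(The first two data columns refer to the binary form. The time-to-event columns score shorter stay as the win.)

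- Cost of the split: 7.3, 6.5, 11.2 and 7.1 points.
- Cost of omitting strata in the analyses as planned: about 0 with moderate effects (−0.5 to +0.7); 3.5 (binary) and 4.8 (time-to-event) with strong effects. Once stay is unsplit, the strong-effect gain is 6.4.

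**5. Cross-check with other assumptions.** With 110 per arm, an 8% shorter stay, 7 points fewer AF interventions and 2,500 trials, power is 18.5% as planned, 19.7% stratified, 23.2% with actual stay and 25.1% with both. The split costs 4.7 points and omitting strata 1.2. Ties are 22% of all pairs, which by step 2 implies that about 44% reach stay.

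**6. Direction in the time-to-event form.** Components 1 to 4 are adverse events, so later is better; component 5 is discharge, so earlier is better. The SAP does not write down that the rule switches. In the first row, scoring later discharge as the win would take the composite from 1.35 to 1.07, its power from 43.4% to 6.0%, and the stay component from 1.44 to 0.69.

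**The case against.** The information on stay is not lost from the plan. Only the first win ratio splits it. The second uses time to discharge unsplit, and 10.3 also compares stay directly with three ANOVA models and two Van Elteren tests. This stands, and it confines the power loss to one analysis.

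The first analysis is binary by design, so putting actual stay into it makes a hybrid closer to the second. That is fair as a description, but a hierarchical comparison does not need its last level to be binary.

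The case for strata is weaker than the case against the split. Stratified randomisation already guards against systematic imbalance, two of the three ANOVA models for stay omit surgery type and age group, and the gain is nil unless the strata are strongly prognostic. The documents give no figure for that. This stands, so stratification is a consistency improvement and second in priority.

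A reader might infer that length of stay decides most pairs because death, stroke and rehospitalisation are uncommon. The documents do not support this. AF intervention ranks above stay and is unlikely to be rare when POAF itself is assumed at 47.8% and 27.8%. In the simulations, components 1 to 4 decide about 56–58% of pairs when AF intervention differs between arms.

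A reader might also infer that the time-to-event version would reward longer stays. Nothing in the SAP says so. The binary form flags stay above the median, the study rationale (Protocol 2.1) lists extended stay among the problematic outcomes, and the clinical hypothesis (Protocol 4.1.1) expects a favourable effect on resource use. Shorter stay is evidently the win, and the gap is one of missing wording.

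**Conclusion.** The point holds as a minor efficiency and consistency issue. The median split costs roughly 5 to 11 points of composite power in the first win ratio and leaves about 21–22% of all pairs tied (19.6% if AF intervention does not differ). Omitting the strata costs about 0 to 5 points in the analyses as planned, depending on how prognostic the strata are. The tie fraction follows from the median split itself. Every power figure rests on assumed rates, and baseline power ran from 11% to 61% across scenarios, so the differences show direction and rough size only.

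The plan contains no reversed component, and the second win ratio has no median split. The analysis is an additional one, SAP 10.0 makes no multiplicity adjustment for it, and the primary result is unaffected.

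**What to change.** In order of priority, in SAP 10.3:

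1. In the first win ratio, keep components 1 to 4 binary and use actual length of stay as the last tie-breaker.
2. Stratify both win ratios by valve surgery and age group. Compare within stratum only and pool with Mantel-Haenszel-type weights: win ratio = Σ wₛ·(win proportion)ₛ / Σ wₛ·(loss proportion)ₛ, where wₛ = nₛmₛ/(nₛ+mₛ).
3. As a clarification, state the winning direction for each component, with earlier discharge alive as the win for stay in the time-to-event version. The word alive matters for the separately reported stay component. SAP 10.3 says "The date/time of death will be used to derive hospital length of stay for participants who died at the hospital", so an early in-hospital death could otherwise count there as a favourable short stay. In the composite, death ranks first and limits this.

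The cost is SAP wording and a small programming change, with no new data. There are three downsides. The first analysis is no longer purely binary. Stay, the lowest-ranked component, decides more pairs, and the estimate moves slightly towards 1 (median 1.43 to 1.38 in the first simulated scenario) although power rises. Stratification also uses fewer pairs: with 100 per arm in four equal strata (assumed), 4 × 25 × 25 = 2,500 instead of 100 × 100 = 10,000.
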